11.2 Pharmacokinetic Studies

Trough level (22-24 hrs after pazopanib dosing): A blood sample will be drawn to assess the trough plasma pazopanib concentration during the 14 day Run-in period of pazopanib monotherapy (2 samples), after completion of adjuvant chemotherapy (2 samples), and every 3 months thereafter until completion of pazopanib maintenance therapy (4 samples). If all trough levels are drawn, a total of 8 samples are possible in a single subject. The trough levels will be compared for any differences over time and will be correlated with the change in SUV from FDG PET and with the change in RECIST measurements on MRIs.

In subjects consenting to the optional full intensive pharmacokinetic visit during Weeks 2-4 following surgery/adjuvant chemotherapy, blood will be obtained at the following timepoints: immediately before pazopanib dosing (within 5 minutes before giving pazopanib on the day of PK dosing) and 1, 2, 3, 4, 6, 8 hour timepoints (+/- 10 minutes), and 24 hrs (range 22 to 24 hours) after dosing (a total of 8 samples/subject).

Pazopanib pharmacokinetic parameters of maximum observed plasma concentration (C_{max}), the time to C_{max} (peak time, T_{max}), the area under the plasma concentration-time curve (AUC_{0-24hr}), concentration at the end of the dosing interval (C_{tr}), oral clearance (CL/F), volume of distribution (Vd/F), and half-life (t_{1/2}) will be determined using noncompartmental methods. The correlation between trough concentrations and AUC will also be evaluated.

11.3 Efficacy Variables

11.3.1 FDG Criteria for Tumor Response

Determination of SUV (SUV lean or SUL) of the primary tumor and metastases will be performed, for up to 5 target lesions, and for non-target lesions. FDG changes of more than 25% from baseline cannot be attributed to the imprecision of the technique and are therefore regarded as true changes in tumor glucose metabolism.[54] FDG criteria for tumor response will be as per the PET Response Criteria in Solid Tumors (PERCIST) criteria.[54] PERCIST includes a specific percentage reduction in the SUV (SUV lean, or SUL) from baseline. Response to therapy is assessed as a continuous variable and expressed as percentage change in SUL peak (or sum of lesion SULs) between the pre- and post treatment scans. A complete metabolic response is defined as visual disappearance of all metabolically active tumor. A partial response is considered more than a 30% and a 0.8-unit decline in SUL peak between the most intense lesion before treatment and the most intense lesion after treatment, although not necessarily the same lesion. More than a 30% and 0.8-unit increase in SUL peak or new lesions is classified as progressive disease.

11.3.2 RECIST Criteria for Tumor Response

Response criteria will be assessed using RECIST (version 1.1).[55]

Evaluation of target lesions:

Complete Response (CR): Disappearance of all target lesions

Partial Response (PR): At least a 30% decrease in the sum of the longest diameter (LD) of target lesions, taking as reference the baseline sum LD

Progressive Disease (PD): At least a 20% increase in the sum of the LD of target lesions, taking as reference the smallest sum LD recorded since the treatment started or the appearance of one or more new lesions

Stable Disease (SD): Neither sufficient shrinkage to qualify for PR nor sufficient increase to qualify for PD, taking as reference the smallest sum LD since the treatment started

Evaluation of best overall response:

The best overall response is the best response achieved prior to surgical resection of the target lesion.

Target Lesions	New Lesions	Overall Response
CR	No	CR
PR	No	PR
SD	No	SD
PD	Yes or No	PD
Any	Yes	PD

Note:

In some circumstances, it may be difficult to distinguish residual disease from normal tissue. When the evaluation of complete response depends upon this determination, this will be determined at the time of surgical resection.

11.3.3 Pathologic Response at Surgery

All specimens of primary tumor will be examined for pathologic response at the time of surgery. The study pathologist will estimate the amount of viable tumor, and report the percentage of necrosis. For purpose of analysis, tumors will be classified as either ≥95% necrosis or <95% necrosis.

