The sole randomized trial conducted in the neoadjuvant setting showed no survival advantage in those patients treated with a doxorubicin/ifosfamide based-regimen versus no chemotherapy.[7] However, this trial was small and may have been underpowered to show a survival benefit. In addition, lower doses of doxorubicin (50 mg/ m^2) and ifosfamide (5 gm/ m^2) for each cycle were administered, compared to what would now be considered optimal dosage of these drugs.

There are practical and theoretical advantages to offering neoadjuvant chemotherapy for patients with large high-risk extremity sarcomas. Neoadjuvant chemotherapy may act in the early systemic treatment of micrometastases and improve outcome for subgroups of patients. In one retrospective study combining data from Dana Farber and Memorial Sloan Kettering, neoadjuvant chemotherapy with doxorubicin and ifosfamide provided a disease specific survival benefit for patients with tumors larger than 10 cm. [8] In some cases neoadjuvant chemotherapy can downsize tumors and improve resectability. Neoadjuvant chemotherapy allows the tumor to be used as a measure of response *in-vivo*, by performing imaging studies before and after treatment. Finally, there is prognostic value to treatment induced pathologic necrosis. A study by Eilber and colleagues from UCLA utilizing neoadjuvant chemotherapy and radiation therapy showed that soft tissue sarcoma patients having 5% or less residual viable tumor (at least 95% tumor necrosis) after therapy at the time of surgery had a significantly lower risk for local recurrence and improved overall survival.[9]

While chemotherapy in adult soft tissue sarcoma may improve outcome for some patients with localized disease, there is a compelling need to develop better control of soft tissue sarcoma dissemination by systemic approaches. Even doxorubicin and ifosfamide, the two most active agents in soft tissue sarcoma, result in frequent tumor recurrence and progression after initial responsiveness.

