2.7 Imaging Studies to Determine Early Response to Therapy in Soft Tissue Sarcoma

Chemotherapy may improve the chance for a cure in patients with high risk sarcomas (intermediate to high grade, ≥ 5 cm), but does not benefit every patient and is associated with toxicities.[3,4] Identifying sarcoma patients who are likely to benefit from neoadjuvant and/or adjuvant systemic treatment has been challenging. In most current trials of anticancer drugs, the objective radiographic response of tumor to treatment, as defined by the international Response Evaluation Criteria in Solid Tumors (RECIST), is used as a surrogate measure for therapeutic benefit.[45] The assessment of soft tissue sarcoma response to chemotherapy is difficult, however, because sarcomas are heterogeneous tumors and consist of varying degrees of cellularity, fibrous septa, stroma, and necrosis. The beneficial effects of a therapy which is successful at eradicating neoplastic cells may be masked by a tumor mass that does not shrink or even grows due to necrosis or intratumoral hemorrhage.[46] Standard radiologic response defined by a change in the size of the tumor to preoperative chemotherapy has not correlated consistently with histologic results at surgery or with survival.[47-49]

FDG-PET: Positron emission tomography (PET) using 18F-fluorodeoxyglucose (FDG), is a tool for evaluation of treatment response in sarcoma. In neoadjuvant therapy for high grade localized sarcomas, serial FDG-PET is a sensitive method to assess early response to therapy; pretreatment standardized uptake value (SUV) and change in SUV predict outcome.[50,51] Eary and colleagues first used FDG-PET in sarcomas and demonstrated the relationship between the quantitative value of the FDG metabolic rate of tumor and the semi-quantitative measure of tumor uptake, the SUV.[52] Eary and colleagues showed that a higher tumor maximum SUV at diagnosis correlated with a greater risk for disease progression and death from disease in patients with soft tissue or bone sarcomas.[50] In a later study, Schuetze and colleagues found that the pretreatment tumor maximum SUV and change in maximum SUV after neoadjuvant chemotherapy independently identified

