3.2 Secondary Objectives

- To examine the activity of antiangiogenic therapy with pazopanib combined with pre-operative chemotherapy for high risk extremity soft tissue sarcomas as measured by: Histological necrosis at surgery
Change in plasma and tumor biomarker assays of angiogenesis
- To evaluate the safety of sequential treatment with pazopanib and pre-operative chemotherapy with doxorubicin and ifosfamide.

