4.2.2 Secondary Endpoints

- Safety profile
- Pathologic response at the time of surgery as measured by % tumor viability
- Progression free survival and overall survival
- Change in plasma and tumor angiogenic biomarker levels pre- and postneoadjuvant therapy.

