Descriptive displays of preliminary clinical endpoints (pathologic response, progression-free survival, overall survival) will compare response for the pazopanib and placebo groups, and will investigate the relationship between early pharmacodynamic response (by PET) and clinical endpoints. Response of high-risk soft tissue sarcoma to neoadjuvant chemoradiation therapy was estimated as 52% (38% no residual tumor, 14% ≥ 95 pathologic necrosis) in a series of 496 patients.[9] A smaller series found only 13/46 (28%) with $< 10\%$ viable tumor in surgical specimens following a variety of neoadjuvant regimens.[51] To direct planning of future studies, we will measure the rate of complete pathological response defined as greater than 95% necrosis in the surgical excision specimen. A 90% Wilson (score) binomial confidence interval will be computed for the rate of complete pathological response.

There are no stopping rules planned for toxicity, but safety will be monitored continuously. All subjects who are registered and receive at least one dose of study drug will be included in the safety analysis.

All reported adverse events will be coded using the Cancer Therapy Evaluation Program (CTEP) Common Toxicity Criteria version 4.0. The number and percent of subjects reporting adverse events (all, severe or worse, serious and related) will be quantified. Listings will be provided for all on-study deaths and adverse events that lead to withdrawal from study. Narratives of all serious adverse events and deaths on-study will be provided.

Correlative study assays will be analyzed using descriptive statistics, generally comparing pazopanib and placebo groups. Correlation will also be evaluated between pazopanib trough concentrations and drug exposure over the dosing interval (area-under-the-concentration-curve, AUC) in subjects consenting to the full intensive pharmacokinetic visits.

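### Pathologic response is listed as percent tumor viability but classified on percent necrosis, with two different cutoffs and no rule for specimens that have little viable tumor yet are not necrotic

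*Combined protocol and SAP*

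**What the plan says.** The plan describes this endpoint in several places, and not in the same terms.

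- Section 3.2 (secondary objectives) names "Histological necrosis at surgery".
- Section 4.2.2 (secondary endpoints) lists "Pathologic response at the time of surgery as measured by % tumor viability".
- Section 11.3.3 sets out the reading: "The study pathologist will estimate the amount of viable tumor, and report the percentage of necrosis". It then gives the analysis rule: "For purpose of analysis, tumors will be classified as either ≥95% necrosis or <95% necrosis".
- Section 14.1 defines the rate to be reported as "complete pathological response defined as greater than 95% necrosis in the surgical excision specimen" and attaches a 90% Wilson interval to it, to help plan later studies.
- Section 14.1 also gives two historical figures. In the first, response "was estimated as 52% (38% no residual tumor, 14% ≥ 95 pathologic necrosis) in a series of 496 patients". The second is 13/46 (28%) with less than 10% viable tumor.
- Section 2.1 describes a favorable result in a cited series as "5% or less residual viable tumor (at least 95% tumor necrosis", treating the two measures as one.

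No section says how to score a specimen that has no viable tumor but is partly fibrotic, or one in which no tumor remains.

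**The concern.** Percent viable and percent necrosis are complementary only if all non-viable tissue is necrotic. If some of it is fibrosis or stroma, a specimen can have almost no viable tumor and still fall short of 95% necrosis. If no tumor remains, there is nothing in which to measure a necrotic fraction. The rule in 11.3.3 and 14.1 names neither case.

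This rate is the only efficacy proportion for which 14.1 specifies an interval. If its value depends on how the pathologist understands the word necrosis, it is not reproducible. Nor is it clearly on the same definition as the 52% it sits beside, which has no residual tumor as a separate response category.

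**Working it through.** **1. The plan's own figures.** 38% + 14% = 52%, and 13/46 = 28.3%. Both agree with 14.1.

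**2. Scoring example specimens.** Let viable + necrosis + fibrosis/stroma = 100% of the tumor area. The specimens are hypothetical.

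| Specimen | ≤5% viable | 11.3.3 literal (≥95% necrosis) | 14.1 literal (>95% necrosis) | Necrosis read as 100% minus viable |
|---|---|---|---|---|
| A: 2% viable, 98% necrosis | response | response | response | response in both sections |
| B: 0% viable, 60% necrosis, 40% fibrosis/stroma | response | non-response | non-response | 100%: response in both |
| C: no residual tumor | response (0% viable) | no stated score; not ≥95% necrosis if taken literally | same | 100%: response in both |
| D: 5% viable, 95% necrosis | response | response | non-response | 95%: still differs between sections |

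B and C depend on the reading of necrosis. D conflicts under either reading. The literal error runs one way: necrosis ≥95% forces viable ≤5%, but not the reverse, so a necrosis-based rate cannot exceed the rate based on ≤5% viable.

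**3. How much could turn on B and C.** The only split the documents offer is the first benchmark in 14.1. Of its 52 response points, 38 are no residual tumor: 38/52 = 73%. Apply that split to 21 specimens (the planned enrollment, all resected and pooled across arms) and vary the share of no-residual-tumor specimens scored as response:

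- All counted: 0.52 × 21 = 10.92, about 11.
- Half counted: (0.14 + 0.19) × 21 = 6.93, about 7.
- None counted: 0.14 × 21 = 2.94, about 3.

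The 90% Wilson interval, with p = x/n, z = 1.645 and z² = 2.706, is

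[p + z²/(2n) ± z·√(p(1−p)/n + z²/(4n²))] / (1 + z²/n).

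For n = 21, z²/(2n) = 0.0644, z²/(4n²) = 0.00153 and 1 + z²/n = 1.1288.

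- x = 11, p = 0.524: center 0.5882/1.1288 = 0.521; half-width 1.645 × √(0.01188 + 0.00153)/1.1288 = 0.169; interval 35% to 69%.
- x = 7, p = 0.333: center 0.3977/1.1288 = 0.352; half-width 1.645 × √(0.01058 + 0.00153)/1.1288 = 0.160; interval 19% to 51%.
- x = 3, p = 0.143: center 0.2073/1.1288 = 0.184; half-width 1.645 × √(0.00583 + 0.00153)/1.1288 = 0.125; interval 6% to 31%.

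The two extreme intervals do not overlap.

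**4. What is not affected.** The sample size in 14.2 rests on percent change in SUV (SD 20%, 0% versus a 30% decrease, n = 21, 2:1). A normal approximation with 7 and 14 patients and an assumed two-sided alpha of 0.05 gives power 0.900, as stated. Pathology does not enter that calculation.

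**The case against.** The strongest reply is that the plan uses viability and necrosis as two names for one quantity. Section 2.1 equates them outright. Section 11.3.3 has the pathologist estimate viable tumor and then report necrosis, which reads naturally as 100% minus viable. Section 3.2 names necrosis, so scoring on it does not depart from the stated objective. Section 14.1 counts no residual tumor within its response benchmark, and failing such a specimen for complete pathological response would sit oddly in the same paragraph.

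Much of this stands. A reader might infer that the plan scores the best responders as failures. The documents do not support that: no section says so, and 2.1 points the other way. Section 2.7 does say that "sarcomas are heterogeneous tumors and consist of varying degrees of cellularity, fibrous septa, stroma, and necrosis", but the sentence explains why imaging response is hard to judge; it is not a rule for reading resection specimens. It shows only that tissue other than viable tumor and necrosis is expected.

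A reader might also take 14% versus 52% as the likely bias. That is unsupported too. The split comes from a neoadjuvant chemoradiation series, whereas pre-operative radiation here is optional (Section 7.0, note D). The documents do not show whether that series' no-residual-tumor group was necrotic. If necrosis is read as 100% minus viable, the effect on specimens B and C is zero.

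The reply does not remove two things. The intended reading has to be inferred, and ≥95% in 11.3.3 conflicts with greater than 95% in 14.1 on any reading.

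**Conclusion.** The concern holds as a matter of definition. The listed endpoint is viability, the analysis rule is necrosis, and specimens with little or no viable tumor that are not at least 95% necrotic can be scored as non-responses if the rule is applied as written. The cutoff also differs between 11.3.3 and 14.1 at exactly 95%, and the stricter 14.1 rule does not match the ≥95 category in its own benchmark. Sections 2.1 and 14.1 together suggest that residual viability was meant.

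The possible size ranges from no effect on specimens B and C, if necrosis means 100% minus viable, to 11/21 becoming 3/21. The upper end assumes the cited series' split, 21 resected specimens, and every no-residual-tumor specimen failed. It bounds the ambiguity and is not a forecast. The endpoint is secondary and descriptive, with no test attached. The change is worth making because the rate is meant to inform later trials and the repair is cheap.

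**What to change.** In 11.3.3 and 14.1, use one definition: pathologic response is ≤5% viable tumor in the resection specimen. State that no residual tumor counts as 0% viable and that fibrosis and stroma are not counted as viable. Keep percent necrosis as a descriptive item, and align the wording of 3.2 with 4.2.2. A single cutoff also removes the conflict at exactly 95%.

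The ≤5% cutoff still differs from the second benchmark (<10% viable). Recording percent viable as a number would allow that proportion to be tabulated as well.

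The cost is wording only. The study pathologist already estimates viable tumor under 11.3.3, so no extra reading is needed, and sample size, power and the primary analysis do not change.

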11.3.4 Duration of Response/Stable Disease

The duration of overall response is measured from the time measurement criteria are met for CR or PR (whichever is first recorded) until the first date that recurrent or progressive disease is objectively documented (taking as reference for progressive disease the smallest measurements recorded since the treatment started).

The duration of overall CR is measured from the time measurement criteria are first met for CR until the first date that recurrent disease is objectively documented.

Stable disease is measured from the start of the treatment until the criteria for progression are met, taking as reference the smallest measurements recorded since the treatment started.

11.3.5 Definition of Disease Progression

Disease progression will be defined as:

- Radiologic progression of disease by FDG PET PERCIST 1.0 criteria
- Radiologic progression of disease by RECIST (version 1.1) criteria.

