7.5 Duration of Therapy

Treatment should continue until the end of protocol therapy, defined as the completion of all adjuvant treatments following surgical resection of the primary tumor, or until one of the following criteria applies:

- Disease progression,
- Intercurrent illness that prevents further administration of treatment,
- Unacceptable adverse events(s),
- Greater than 3-week delay in therapy due to adverse event
- The subject or legal representative requests to withdraw from the study, or
- Changes in the subject's condition render the subject unacceptable for further treatment in the judgment of the Investigator.

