7.6 Duration of Follow-Up

When a subject discontinues the study, a Final Visit will be conducted. All subjects will have one Follow-up Visit approximately 30 days after the Final Visit. This Follow-up Visit does not need to be performed for subjects who have had a Final Visit conducted \geq 30 days after discontinuation of maintenance pazopanib therapy.

Study visits and evaluations will be performed in clinic at Screening and within approximately 72 hours prior to hospital admission for each chemotherapy cycle (neoadjuvant as well as adjuvant). Assessments will include interval history, physical examination, blood counts and chemistries. Radiological assessments including FDG-PET CT, MRI of the primary tumor, and diagnostic CT chest will be performed prior to the 14 day Run-in period of pazopanib versus placebo. After the Run-in period, and prior to commencement of preoperative chemotherapy, subjects will undergo repeat FDG-PET CT and MRI of the primary tumor. After 2 cycles of chemotherapy, FDG-PET CT and MRI of the primary tumor will be repeated. (**Refer to Section 4.3 and Appendix A**). Study procedures may be performed up to approximately 72 hours before or after the scheduled visit date.

Subjects will be evaluated daily during radiation therapy. Following surgery, subjects who remain on pazopanib monotherapy will have study visits and evaluations monthly for the one year duration of therapy, and follow-up visits will be every 3 months for those not on pazopanib. CT of the chest without contrast will be performed every 3 months for the first

year following surgery and MRI (or CT) of the primary site of the tumor will be performed every 6 months.

Following the Final Visit and/or 30-day Follow-up Visit, follow-up will proceed as described in the study calendar (Appendix A) until recurrence or progression. Patients experiencing recurrence or progression will be contacted every 4 months for overall survival, unless the patient has withdrawn consent for the study has ended.

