7.8 Criteria for Evaluability and Removal/Withdrawal from Treatment

Criteria for evaluability of the Trial

- Patients must have received a total of at least 80% of the intended dose of doxorubicin, ifosfamide, and pazopanib to be evaluable for the trial. If less than this amount is received, the patient may remain on the study, but will not be evaluated for primary endpoints.

Criteria for stopping therapy:

- Substantial non-compliance with the requirements of the study.
- Any adverse event which, in the Investigator's opinion, requires termination of the study medication.
- Disease progression, unless at the discretion of the Investigator (in collaboration with Novartis) continued treatment with study drug is appropriate.
- The patient would benefit from additional radiation therapy beyond that specified in the protocol.
- Request by the patient or a legal representative/relative to stop the treatment.
- The patient presents with a beta-HCG test consistent with pregnancy. Pregnancy will be reported along the same timelines as a serious adverse event.
- The patient uses illicit drugs or other substances that may, in the opinion of the Investigator, have a reasonable chance of contributing to toxicity or otherwise interfering with results.
- The development of a second malignancy that requires treatment, which would interfere with this study.
- The patient is lost to follow-up.
- Interruption in administration of pazopanib or chemotherapy for greater than 3-week delay.
- Development of an intercurrent illness or situation which would, in the judgment of the Investigator, affect assessments of clinical status and study endpoints to a significant degree.

Criteria for study withdrawal:

- Study closure.
- Patient decision to withdraw from both study therapy and follow-up.

The Investigator will make every reasonable effort to keep each patient in the study unless it is in the patient's best interest to discontinue participation. If a patient is removed from the study or declines further participation, all End of Treatment evaluations should be performed if the patient is willing and able to be assessed. A description of the reason(s) for withdrawal from the study will be recorded on the case report form (CRF). The Investigator should also ensure that all patients are followed up for survival and recurrence after the Final Visit.

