11.3.6 Time-to-Event Measures

Time to Local Recurrence- Defined as the duration of time from surgical resection of the primary tumor until local recurrence (amputated patients excluded).

Local Disease-Free Survival- Defined as the duration of time from surgical resection of the primary tumor until local recurrence or death, whichever occurs first.

Distant Disease-Free Survival - Defined as the duration of time from randomization until development of distant metastatic disease or death, whichever occurs first. Subjects with stage IV disease will be censored from this analysis.

Disease-Free Survival - Defined as the duration of time from surgical resection to local recurrence, distant metastatic disease, or death, whichever occurs first. Subjects with stage IV disease will be censored from this analysis.

Progression-Free Survival - Defined as the duration of time from randomization to progressive disease (per RECIST), local recurrence, distant metastatic disease (exclusive of stage IV subjects), or death, whichever occurs first.

Overall Survival - Defined as the interval of time from randomization until death from any cause.

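### Progression includes a PET criterion in 11.3.5 but PFS counts only RECIST in 11.3.6, so a PET-only rise can end scheduled imaging with no PFS event and may drop an observed primary value

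*Combined protocol and SAP*

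**What the plan says.** Section 11.3.5 defines disease progression with two bullets: "Radiologic progression of disease by FDG PET PERCIST 1.0 criteria" and "Radiologic progression of disease by RECIST (version 1.1) criteria". No conjunction joins them. The PET threshold is in 11.3.1: "More than a 30% and 0.8-unit increase in SUL peak or new lesions is classified as progressive disease".

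Section 11.3.6 defines PFS more narrowly, as the "duration of time from randomization to progressive disease (per RECIST), local recurrence, distant metastatic disease (exclusive of stage IV subjects), or death". PERCIST is not named there.

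Progression has operational consequences elsewhere:

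- Section 7.5 continues treatment to the end of protocol therapy "or until one of the following criteria applies"; disease progression is the first criterion listed.
- Section 7.8 lists progression as a reason to stop therapy, with an exception at the investigator's discretion.
- Section 7.6 runs calendar follow-up until recurrence or progression, after which "Patients experiencing recurrence or progression will be contacted every 4 months for overall survival".
- Section 7.8 separately asks the investigator to follow all patients for survival and recurrence after the Final Visit, without an imaging schedule.

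On evaluability, 7.8 requires at least 80% of the intended doxorubicin, ifosfamide and pazopanib, and adds: "If less than this amount is received, the patient may remain on the study, but will not be evaluated for primary endpoints". Section 11.0 applies the 80% rule to the first two chemotherapy cycles. Section 14.1 takes the primary endpoint as percent change in SUV from baseline to the end of the run-in. It expects to exclude patients with incomplete data from missed PET scans or withdrawal for toxicity.

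**The concern.** A patient whose SUL peak rises past the threshold while the MRI shows no RECIST progression has progressed under 11.3.5 but has had no PFS event under 11.3.6. Followed literally, the plan can stop that patient's therapy and scheduled imaging at that moment. A later non-fatal PFS event may then be found late or not at all.

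Two features make this more than a wording matter. Section 2.7 itself says that size change is an unreliable guide to response in sarcoma, so PET and RECIST can be expected to disagree at times. Section 14.1 also plans to display PFS against early PET response, so the loss of follow-up would be triggered by the same variable that serves as the predictor.

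The second consequence concerns the primary comparison. A patient stopped at the run-in PET has had no chemotherapy and cannot meet the 80% rule, yet the primary endpoint is fully observed by then. The outcome would be deciding whether it enters its own analysis.

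**Working it through.** **1. The text, side by side**

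| Use | Criterion in the plan | Section |
|---|---|---|
| Definition of progression | PERCIST 1.0 and RECIST 1.1, both listed | 11.3.5 |
| PFS event | RECIST progression, local recurrence, distant metastasis (not for stage IV), death | 11.3.6 |
| End of therapy | Progression, unqualified | 7.5; 7.8 (with discretion) |
| End of calendar follow-up | Recurrence or progression, unqualified | 7.6 |

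Since the last two rows name no criterion, the general definition in 11.3.5 applies to them. Reading its bullets as alternatives is the natural reading; 11.4 accepts either criterion for response. If both were required, 11.3.5 and 11.3.6 would still differ, because RECIST alone is a PFS event.

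**2. Where the gap can arise**

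After baseline, PET is scheduled only at the end of the run-in and after two chemotherapy cycles (11.1, Appendix A). A distant lesion first seen on PET in a patient without stage IV disease is already a PFS event. What remains is an SUL-peak rise without RECIST progression, plus PET-only new lesions in stage IV patients.

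**3. The plan's own figure**

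Inputs from 14.2: SD 20, mean change 0 (placebo) and -30 (pazopanib), n = 21 at 2:1, hence 7 and 14. The variable's name is missing from that sentence; I take it to be SUV. The test is two-sided (14.1). Alpha is not stated; 0.05 is assumed.

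- Standard error = 20 × √(1/7 + 1/14) = 9.26
- Power = Φ(30/9.26 − 1.96) = Φ(1.28) = 0.90

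This reproduces the stated figure of about 90%.

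**4. How often a day-14 rise above 30% would occur**

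Same inputs, normality assumed, 0.8-unit condition ignored:

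- Placebo: 1 − Φ(30/20) = 1 − Φ(1.5) = 0.0668
- Pazopanib: 1 − Φ(60/20) = 1 − Φ(3) = 0.0013
- Expected number: 7 × 0.0668 = 0.47 placebo; 14 × 0.0013 = 0.02 pazopanib
- At least one among 7 placebo patients: 1 − 0.9332⁷ = 0.38
- At least one among all 21: 0.40

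For an assumed SD of 15 to 30, the placebo rate runs from 2.3% to 15.9%, and the chance of at least one among 21 from 15% to 78%.

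**5. Effect on the primary comparison if every such patient were excluded**

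- Placebo mean after truncation at +30: −20 × φ(1.5)/Φ(1.5) = −20 × 0.1295/0.9332 = −2.8
- Pazopanib shift: −20 × φ(3)/Φ(3) = −0.1
- Expected difference: 30 − 2.8 + 0.1 = 27.3 points

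Simulating the exact two-sided Wilcoxon test on normal data (20,000 runs) gives power of about 84% with all patients and about 78% with these patients removed.

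Steps 4 and 5 give upper bounds. The 0.8-unit rise is also required, some of these patients would also meet RECIST progression, and the investigator may continue treatment. The rate after two chemotherapy cycles cannot be computed from the documents.

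**The case against.** The strongest reply is that 11.3.6 is unambiguous about the PFS event, and an endpoint may properly be narrower than a general definition. That is right: the PFS definition needs no change. What is missing is a link from 11.3.5 to 7.5, 7.6 and 7.8 that keeps imaging going until the PFS event.

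Three stronger readings are tempting, and the documents do not support them.

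- *A reader might infer that these patients are censored in PFS.* The plan gives no PFS censoring rule. Censoring at the last scan would be usual, and here informative, but it is an inference.
- *A reader might infer that all RECIST and recurrence information is lost.* MRI accompanies both post-baseline PETs, and 7.8 asks for recurrence follow-up in all patients. That request has no imaging schedule and does not match 7.6, so it softens the gap without closing it.
- *A reader might infer that the primary analysis is certain to lose these patients, or is tilted toward pazopanib.* Section 14.1 lists missed scans and withdrawal for toxicity as the expected exclusions, and a patient with both scans who stops for PET progression fits neither. Sections 7.8 and 11.0 therefore conflict with 14.1, and exclusion is not settled. If it happened, the shift would be toward the null.

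It is also fair that aligning the progression definitions would not remove the 80% rule. That rule needs its own sentence in the fix. Finally, PFS is secondary, is not among the objectives in section 3, and receives only descriptive displays.

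**Conclusion.** The mismatch stands in the current text. A PERCIST-only rise at one of two pre-operative scans can end scheduled imaging without a PFS event, and the plan does not say how PFS then treats the patient. The effect on PFS is limited, because the endpoint is secondary and descriptive and few patients are likely to be affected.

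The primary analysis is exposed only if therapy is stopped before chemotherapy and 7.8 and 11.0 are followed over 14.1. In that case up to about 6.7% of placebo patients would be removed because of their own outcome, and the planned difference would fall from 30 to about 27 points. This rests on the 14.2 means and SD and on normality. The loss would be in power and would not create a false benefit, but with 7 placebo patients a single exclusion is 1/7 = 14% of that arm. The point should be settled before analysis.

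**What to change.** Three statements would close the gap.

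1. RECIST remains the progression criterion for PFS, as 11.3.6 has it. A PERCIST-only increase is reported descriptively, is not a reason to censor PFS, and does not end scheduled RECIST imaging or recurrence follow-up.
2. Every randomised patient with a baseline and a day-14 PET enters the primary comparison, whatever chemotherapy dose follows. Sections 7.8, 11.0 and 14.1 should be brought into line with this.
3. Sections 7.5, 7.6, 7.8 and 11.3.5 are reconciled on which definition of progression ends treatment and which ends follow-up. The clinical rule is for the investigators; this review does not propose one.

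The cost is wording, plus continued scheduled imaging in the few patients affected.
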